Exercise-based lifestyle interventions aimed at counteracting treatment-induced adverse effects have been shown to be safe and effective in improving bone, functional and cardiometabolic health for patients with PCa.(19, 20) However, men, in general, are harder to engage in physical activity (PA) and lifestyle interventions.(3, 21) As an alternative to traditional exercise programs, recreational team sports provide a unique environment that may lead to increased physical activity participation and motivation to engage in other lifestyle changes.(22) Results from a recent meta-analysis by our group suggest that community-based, recreational team sports interventions lead to significant improvements in weight, waist circumference, body fat percentage, lipids, blood pressure and measures of fitness, with a greater change in males vs females.(23) More than any other sport, recreational soccer (RS) has been shown to be a successful health intervention in patients with, or at risk of chronic diseases,(24-26) including PCa.(27, 28) While soccer is extremely popular in many countries outside of the U.S. and has been found to dramatically improve health in PCa patients,(27, 29) soccer has only recently begun to gain popularity in the U.S., especially among men. Therefore, there is a need to develop implementation science strategies to adapt these interventions that can enhance adherence to lifestyle interventions in a population that stand to benefit greatly from a physical, phycological and mental health perspective.

Leveraging the growing enthusiasm around soccer in Atlanta and the U.S. may lead to increased interest, participation, retention and engagement in lifestyle change programming among PCa survivors. Therefore, this study seeks to directly test the implementation feasibility of a soccer-based lifestyle change intervention vs a low-cost mobile-health (mHealth) enabled lifestyle intervention and determine their effects on bone health, body composition, mental health, functional and cardiometabolic status among PCa survivors.

Bone health is of particular interest among PCa survivors given the ADT-related declines in BMD and increased risk of fractures, an independent factor inversely associated with disease survival independent of disease stage.(13) A recent meta-analysis that included five prospective cohort studies with a total of 533 patients, evaluated the change in BMD in patients with PCa receiving ADT, compared to those with PCa or other urologic conditions not receiving ADT.(14) The mean difference of percent change in BMD in the ADT treatment vs control group in the lumbar spine (BMD -3.60, 95% CI -6.72 to -0.47, $P = 0.02$) shows that there is a statistically and **clinically significant relationship between ADT and BMD reduction in patients with PCa** and that strategies to counteract BMD loss should be considered in patients with PCa undergoing ADT.(14) Further, changes in BMD have been detected with PA interventions within six months.(30, 31)

Soccer has been shown to be a **successful vehicle to deliver health interventions**.(32, 33) **Soccer is the most popular** sport in the world and an important staple of social interaction globally, with over 500 million active registered participants worldwide and nearly 16 million in the US.(32, 33) Recreational soccer, can be effective to reduce cardio-metabolic risk in both children and adults through varied movement patterns and highly functional training.(26, 34) Generally, there are close to 100 high-intensity short runs and other specific intense actions over a 1-hour training session, with average heart rates around **80% of maximal heart rate, irrespective of age, fitness status and previous soccer training experience**.(35) These high intensity intervals (HIIT) reduce insulin resistance, chronic inflammation and arterial stiffness.(36) Proper screening and RS programming delivered by trained **“Football (soccer) Medicine”** coaches are **safely tolerated** by middle-aged and older adult participants with **hypertension, obesity, diabetes and cancer**.(28, 37-40) Despite the high heart rate, small-sided RS had the lowest perceived exertion rate compared to interval running.(41) This may contribute to the high **adherence rates (> 90%), long-term retention** and high enjoyment seen in RS

interventions.(35, 42) In addition, adding a functional warm-up program, has shown to reduce injuries by 40%.(43-46). RS also builds social capital and is associated with positive motivational factors.(47) The physiologic and behavioral aspects of RS associated with health improvements are summarized by the Football (soccer) is Medicine collaborative we belong to.(24)

Protocol Synopsis

Study Design: A randomized controlled trial to compare two lifestyle intervention deliveries and their effect on bone health and diet and physical activity related measures.

Planned Sample Size: 20 subjects

Subject population: Inclusion criteria: 1) Men aged 18-79 years; 2) PCa survivors that had at least 6 months of hormone therapy (i.e. ADT with testosterone lowering agents) within the past 10 years; 3) not engaged in soccer practice or other exercise or lifestyle intervention program for the past 12-months; 4) Availability of smartphone to receive text messages; 5) Treating Oncologist clearance 6) ability to read in English or Spanish and provide informed consent; **Exclusion criteria:** 1) BMI > 40 kg/m²; 2) resting BP ≥170/100 at screening or uncontrolled hypertension; 3) any mobility issues or exercise program contraindications (48); 4) a recent (i.e., within 12 months) myocardial infarction, diagnosis of congestive heart disease, other active cancer 5) bone or organ metastases, 6) chemotherapy within past 6 months; 7) Therapies and diseases of bone unrelated to PCa e.g. systemic glucocorticoids, bisphosphonates, teriparatide, denosumab, osteomalacia; osteosarcoma; Paget's disease; systemic lupus erythematosus; inflammatory bowel diseases, rheumatoid arthritis; thyroid/parathyroid disorder or mental illness.8) Not COVID-19 vaccinated

Specific Aims

Aim 1: We will conduct a single-arm clinical trial over 3 months, among PCa survivors that had at least 6 months of hormone therapy (i.e. ADT with testosterone lowering agents) within the past 10 years. Participants (n=20) will be offered an intensive intervention including RS programming and lifestyle education. The group will receive RS, consisting of small-sided (5vs5) conditioning drills and games, adapted to the population (60-minute sessions twice/week). We will evaluate pre vs post differences over 3-months in:

(Aim 1a): Primary outcome: lumbar spine BMD at 3-months.

(Aim 1b): Secondary outcomes: impact on additional markers of bone health including total hip BMD and bone turnover markers (Osteocalcin (a marker of bone formation) and C-terminal telopeptide of collagen (CTX) a bone resorption marker), body composition (weight, BMI, % body fat, waist circumference, lean body mass), cardiometabolic markers (resting heart rate and blood pressure), functional markers (aerobic capacity, muscle strength), behavioral factors (diet and PA self-efficacy, dietary intake, smoking and alcohol habits, weekly steps, sedentary and sleep time) and patient-reported quality of life and depression symptoms.

Aim 2: To assess implementation feasibility and evaluate overall efficacy to increase engagement and adherence with PA, we will evaluate between-group differences over 3 months in:

(Aim 2a): compliance with recommendations of 150 minutes of moderate-to-vigorous PA/week.

(Aim 2b): To assess the RS program adherence and tolerance, we will monitor session attendance, attrition rates, injuries or adverse events, use surveys for assessing participant program satisfaction and behavior change self-efficacy

Research Design:

Organizational structure of study team: This study was investigator initiated and proposed to the Winship Cancer Institute prostate cancer funding opportunity at Emory University as part of an internal pilot grant. The funder's expectation was for the investigator to conduct feasibility or pilot research to support a larger grant. Funder will provide a speedtype for all expenses related to the study.

Setting: All assessments will be conducted at the Emory University Hospital Georgia CTSA GCRC location (baseline and post intervention). Those randomized to the soccer intervention will attend soccer sessions at a local soccer field (either Dunwoody Elementary or the Atlanta Silverbacks indoor facility), no permission is

needed to conduct the study, but field owners are aware of the study be conducted. All data will be collected on paper and transferred to a REDCap database at Emory University Rollins School of Public Health.

Aim 1. Experienced soccer coaches will be identified and hired from the local area to deliver the soccer program. These coaches will be trained in two key aspects of the program: 1) leading small-sided recreational soccer training designed to safely engage participants in HIIT conditioning; 2) facilitate the lifestyle education by devoting time during each soccer training session to reviewing the material (based on Life's Simple 7 topics), fostering discussion and using the groups' social dynamics to promote sustained lifestyle behavior change and increase self-efficacy. These coaches will be the primary facilitator of the study, conducting both soccer specific activities and education discussion. The study staff will conduct consent and all measurements and assessments.

Recruitment: Participants will be recruited from the Emory Oncology clinics and if needed Georgia Urology through our Winship Cancer prostate cancer physicians and Kaiser Permanente and using the recruitment flyer. Interested participants will be screened over the phone to determine eligibility based on inclusion and exclusion criteria above. Those meeting inclusion criteria will be scheduled for baseline assessments at the Georgia CTSA research center. Participants meeting inclusion and exclusion criteria will be invited to participate in the study.

Study Assessments. Prior to testing, subjects will be asked to refrain from physical activity for 48 hours prior to test day, refrain from alcohol 24 hour prior to testing, and refrain from caffeinated drinks, smoking and other stimulants one hour prior to testing. Assessments will be conducted at baseline and post intervention at the Emory University Hospital Georgia CTSA research center (GCRC). Blood pressure, both systolic and diastolic blood pressure will be measured while sitting using a calibrated electronic blood pressure sphygmomanometer prior to any activity and after five minutes of rest., height and weight, waist circumference, aerobic and musculoskeletal fitness assessments will be performed. Bone mineral density will be measured by dual x-ray absorptiometry (DXA) scan at the lumbar spine (L2-L4) and total hip. Body composition will also be determined by DXA scan in the Bionutrition Unit of the GCRC. Venipuncture will be performed by the research nurse for bone turnover markers (Osteocalcin (a marker of bone formation) and C-terminal telopeptide of collagen (CTX) a bone resorption marker), a total testosterone level if not included in a recent clinic visit, and to bank one tube of plasma for future metabolomics studies. In addition, questionnaires will be used for self-reported physical and mental health, quality of life, PA and diet self-efficacy, program satisfaction and injuries. Dietary recalls will be conducted at baseline and 26 weeks by trained staff and analyzed using Nutrition Database System for Research.(49) In addition, both groups will also be asked to wear a Garmin fitness tracker for the duration of the study to measure steps and moderate and vigorous activity. Once baseline measurements are complete and 20 participants have completed they will be randomized to either the soccer group or the mobile health (mHealth) group. Participants in the soccer group will participate in soccer drills and other fitness routines (two 1-hour sessions per week). They will meet with the soccer coach after the soccer sessions to discuss the lifestyle education topics (Life's Simple 7 education topics). During the soccer sessions participants will be fitted with a wearable soccer-specific device to measure how much they move and their heart rate.

Informed Consent Process:

Adult consent forms will be prepared for this study. The consent form will describe the purpose of the study, the procedures and risks. Participant will be presented with the consent form by the trained study staff, in person and given time to read and ask questions. A signed consent form will be obtained from the participant. A copy of the consent form will be given to the participant and this process will be documented.

Risks:

There is minimal risk in this study. Potential risks are related to 1) Venipuncture and Finger sticks 2) Dual x-ray absorptiometry (DXA scan) 3) Physical injury related to sport and 4) Confidentiality. 1) A single-use finger stick device will be used during assessments along with alcohol to clean the site prior to stick to reduce chances of infection. Trained research nurses will be used for venipuncture in a clinical setting with proper antiseptic precautions 2) DXA involves exposure to small amounts of radiation. The radiation dose is equal to or less than the amount of background radiation received in a round-trip flight from New York to Los Angeles or the

natural environmental radiation the average person receives in the United States annually. The risk from radiation exposure of this magnitude is considered to be negligible when compared to everyday risks. 3) Exercise can cause muscle soreness, weakness and in some cases muscle strains, ligament sprains and rarely bone fractures can occur. In very rare cases exercise can induce chest pain or a heart attack or other medical emergency. The training program led by the soccer coach is designed to minimize risk of injuries or events by slowly progressing on the practice of soccer using soccer and exercise drills appropriate for your age and level of fitness. Soccer sessions will be led by trained professionals who are able to offer suggestions to limit and prevent these adverse events. They are trained to recognize medical emergencies, will have basic equipment available, and seek emergency care if needed. 4) There is a risk of loss of confidentiality. Efforts will be made to keep all personal information confidential. All data will be stored in locked offices and password-protected computers. Personal identity will be protected in any publication.

Benefits: There are no direct benefits of this study beyond opportunity to exercise and information about healthy behaviors.

Compensation:

Participants will receive a \$20 gift card for each assessment visit plus a parking voucher (total compensation value \$52). Subjects that complete the study will be allowed to keep the Garmin fitness tracker.

Data Analytics and Statistical Plan:

Descriptive analysis will be performed to assess the study primary aims. All statistical tests will be 2-sided, and the significance level will be set at 0.05. Data will be assessed for normality and reviewed for outliers and missing values. Mathematical transformations may be applied to meet normality assumptions. All primary analyses will be performed using the intention-to-treat principle to estimate the effects of the program.

Moreover, we will estimate the intervention efficacy using as-treated analysis, where participants are classified according to the number of sessions actually attended (i.e. the dose-response will be evaluated). To assess the effect of the proposed intervention program between baseline and 3 months, to compare the differences in the changes of the primary outcome of BMD and secondary outcomes, multilevel longitudinal models (MLM) will be used to test for differences time effects while adjusting for attrition and the correlational structure within time (repeated measures). Potential covariates may include potential effects of age, smoking, alcohol use, and therapy type. Attention will also be paid to heterogeneity between subjects (random intercept effects). Given the sample size of 40 subjects, only large effect sizes will be detectable at 80% statistical power. However, the primary focus of the analysis will be to gather initial estimates on the effect sizes (group differences and intervention efficacy) to establish adequate statistical power for a future larger study. **All analysis will be conducted by [name].**

Training of study team:

As stated above all staff and soccer coaches will receive adequate training of all study procedures. All study staff and collaborators will take CITI training upon hire.

Confidentiality: All participants will receive a study ID and this will be used on all paper and electronic forms. We will destroy all identifiers and any audio from key interviews after the study is complete.

References

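### The protocol describes both a single-arm soccer trial and a randomized soccer-versus-mHealth trial, with totals of both 20 and 40, so the primary contrast is undefined

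*Combined protocol and SAP*

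**What the plan says.** All the text is in the combined protocol and SAP.

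- **Background:** the purpose is to test "a soccer-based lifestyle change intervention vs a low-cost mobile-health (mHealth) enabled lifestyle intervention". Randomization is not mentioned here.
- **Protocol Synopsis, Study Design:** "A randomized controlled trial to compare two lifestyle intervention deliveries and their effect on bone health".
- **Protocol Synopsis, sample size:** "Planned Sample Size: 20 subjects".
- **Specific Aims, Aim 1:** "We will conduct a single-arm clinical trial over 3 months, among PCa survivors". All 20 participants are offered soccer with lifestyle education, and "We will evaluate pre vs post differences over 3-months in" the primary outcome, lumbar spine BMD at 3 months, and the secondary outcomes.
- **Specific Aims, Aim 2:** "we will evaluate between-group differences over 3 months in" compliance with 150 minutes of moderate-to-vigorous activity per week (Aim 2a). Aim 2b covers attendance, attrition, injuries and satisfaction with the soccer program.
- **Setting:** "Those randomized to the soccer intervention will attend soccer sessions at a local soccer field".
- **Study Assessments:** after 20 men have completed baseline, "they will be randomized to either the soccer group or the mobile health (mHealth) group". The activity tracker is to be worn by both groups.
- **Data Analytics and Statistical Plan:** a multilevel longitudinal model is to compare differences in changes, yet the test is described as one of time effects. The power sentence assumes 40 subjects and says that only large effects can be detected, with no number. The main stated purpose is to obtain effect-size estimates, including group differences, for a larger study.

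**The concern.** These statements cannot all be true. A study cannot give soccer to all 20 men and also randomize 20 men between soccer and mHealth. The choice decides what is estimated. Under Aim 1 it is a mean change in one treated group; under the Synopsis it is a difference between randomized groups.

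An uncontrolled change cannot separate soccer from background drift in BMD. Eligibility requires at least six months of androgen deprivation at some time in the past ten years, so men may be on or off therapy at entry, and neither the size nor the direction of that drift is known. Two analysts following this plan could report different primary results and draw different conclusions. The planned use of the results suffers too, because a single arm yields no group difference with which to power a two-arm trial.

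**Working it through.** **1. Can the design statements be reconciled?** The Synopsis, Setting and Study Assessments randomize; Aim 1 does not. The model sentence does not settle it. A time effect is the single-arm estimand and a group-by-time effect is the randomized one, but the sentence mixes the two ideas and names no group term.

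**2. Can 20 and 40 be reconciled?** Reading 20 as a per-arm figure would give 40, but the Synopsis gives 20 as the study's planned size, and Study Assessments splits the men into two groups once 20 have finished baseline. So 20 is a total in both places.

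**3. The plan's own power statement.** It gives N = 40 and 80% power; the same section sets two-sided alpha 0.05. It gives no effect size, SD, allocation ratio or dropout, so it cannot be reproduced as a number. I can only ask which design it fits. Assumptions: 1:1 allocation, no dropout, effects in SDs of the three-month change.

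Normal approximation, with z(0.975) + z(0.80) = 1.960 + 0.842 = 2.802:

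- two arms, n per arm: d = 2.802 × √(2/n)
- one arm, before-after: d = 2.802 / √n

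| Design | Formula | Normal | Noncentral t |
|---|---|---|---|
| One arm, 20 | 2.802/√20 | 0.63 | 0.66 |
| One arm, 40 | 2.802/√40 | 0.44 | 0.45 |
| 10 vs 10 | 2.802 × √(2/10) | 1.25 | 1.32 |
| 20 vs 20 | 2.802 × √(2/20) | 0.89 | 0.91 |

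Taking a large effect as about 0.8 SD (a conventional benchmark, assumed here), the sentence about 40 subjects fits 20 versus 20 (0.91). It does not fit one arm of 40 (0.45).

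**4. What if the trial is randomized with 20 in total?** By the t-test, power for the 0.91 SD effect falls from 80% to 49%. At 0.8 SD it is 69% with 20 versus 20 and 40% with 10 versus 10.

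**5. Aim 2a.** The documents give no expected compliance, so I show 50% (the widest case) and 20%, the same in both arms. One arm of 20 has an exact (Clopper-Pearson) interval for its own proportion but no between-group difference. For two arms the Newcombe interval is built from the Wilson limits (l, u) of each arm. With equal observed proportions p its half-width is √[(p − l)² + (u − p)²].

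| Compliance | One arm of 20, exact 95% CI | 10 vs 10, half-width | 20 vs 20, half-width |
|---|---|---|---|
| 50% | 27% to 73% | 37 points | 28 points |
| 20% | 6% to 44% | 34 points | 25 points |

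For example, 5/10 has Wilson limits 0.237 and 0.763, so the half-width is √(0.263² + 0.263²) = 0.37.

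**The case against.** The best defence is that this is a pilot. The statistical plan calls the primary-aim analysis descriptive and puts effect-size estimation ahead of power, and either design could be acceptable for a feasibility study. That is fair, and it means the harm is an undefined estimand rather than a failed confirmatory test. It does not remove the contradiction: the plan still sets two-sided tests at 0.05 and intention-to-treat, and it still wants group differences as an output.

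Several narrower points stand:

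- The power sentence gives no number, and 1.32 SD is also a large effect, so its wording stays literally true at 10 versus 10. The 0.91 SD is inferred here. The sentence is too favourable only if 20 men in total are randomized; one arm of 20 detects 0.66 SD, though of a different quantity.
- A single arm still supplies useful planning inputs: the SD of change, attrition and adherence. What it cannot supply is the group difference.
- Aim 2b can be described within one arm. Only the between-group comparison, clearly Aim 2a, fails.
- If 40 is the intended total, it is the figure of 20 that has to change.

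**Conclusion.** The concern holds and must be fixed. Two incompatible designs and two sample sizes stand in the current text, nothing visible says which governs, and the primary contrast for lumbar spine BMD is therefore not uniquely defined. Aim 2a cannot be carried out under Aim 1's design.

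With 20 men, the detectable effect doubles from 0.66 SD for an uncontrolled change to 1.32 SD for a randomized difference, and these answer different questions. If 40 were randomized it would be 0.91 SD. The figures rest on equal allocation, no dropout and a t-test on change; dropout would make all of them worse. The contradiction itself depends on none of these assumptions.

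**What to change.** State one design and one total sample size in every section, and remove the text that belongs to the other.

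**If randomized:**
- Take the single-arm and before-after wording out of Aim 1.
- Name the between-group difference in lumbar spine BMD at 3 months as primary. Estimate it either from a model of the 3-month value adjusted for baseline, or as the group-by-time term in the longitudinal model with baseline as an outcome row. Choose one in advance.
- Keep the between-group contrast for Aim 2a.
- Give the allocation ratio, the number per arm and, if not described elsewhere, the content of the mHealth arm.

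**If single-arm:**
- Remove the text on randomization, mHealth, both groups and group differences.
- Restate Aim 2a as the proportion reaching 150 minutes per week with an exact 95% interval, and keep Aim 2b as description.
- State that the before-after change is not evidence of efficacy.

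**In either case,** make the power sentence and the Synopsis agree on N, and give the numeric detectable effect for the chosen design.

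**Cost:** a wording amendment, plus allocation and mHealth text if randomized. It needs no extra participants or procedures if 20 is the intended total; if 40 is intended, 20 more men are needed than the Synopsis plans. The single-arm choice gives up the comparative claim. Randomizing 20 means stating a detectable effect of 1.32 SD.

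### Design and sample size conflict; if the trial is single-arm, the pooled 3-month lumbar BMD change is not a programme effect and also moves with an uncontrolled ADT mix

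*Combined protocol and SAP*

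**What the plan says.** The Protocol Synopsis gives the design as "A randomized controlled trial to compare two lifestyle intervention deliveries" and "Planned Sample Size: 20 subjects". Specific Aims, Aim 1, says "We will conduct a single-arm clinical trial over 3 months", offers soccer plus lifestyle education to all 20 men, and evaluates pre versus post differences, with "Primary outcome: lumbar spine BMD at 3-months". Research Design, Setting, returns to two groups: "Those randomized to the soccer intervention will attend soccer sessions at a local soccer field". Study Assessments also randomizes between soccer and mHealth, and Aim 2 speaks of between-group differences.

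Eligibility is "PCa survivors that had at least 6 months of hormone therapy (i.e. ADT with testosterone lowering agents) within the past 10 years". No criterion requires or excludes current ADT.

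The background text on bone health reports a meta-analytic difference in percent BMD change "in the lumbar spine (BMD -3.60, 95% CI -6.72 to -0.47" for men on ADT, "compared to those with PCa or other urologic conditions not receiving ADT". It does not say over what period.

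The Data Analytics and Statistical Plan bases its power remark on 40 subjects. It plans multilevel models of change over time with random intercepts, tested two-sided at 0.05. Of its optional covariates, only an undefined therapy type could bear on ADT. Its main focus is effect-size estimates for a larger study. Study Assessments provides for a total testosterone level where no recent clinic value exists. Neither section gives that value a role in the analysis.

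**The concern.** Two problems meet here. First, the documents do not settle whether there is a comparator or whether N is 20 or 40, so the power remark cannot be tied to a design. Second, under the single-arm wording the primary estimate is a raw change over three months. It combines any programme effect with whatever BMD would have done anyway. The plan's own rationale names ADT as one cause of BMD loss, and eligibility lets exposure to it vary from man to man.

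The effect-size estimate is the intended product of this pilot. If it is carried into the sample size of a larger study, a value that partly reflects the share of men on ADT would be used as if it were the effect of the programme.

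**Working it through.** **1. The plan's power remark.** Inputs: N = 40, 80% power, two-sided 0.05 (statistical plan); N = 20 (Synopsis and Aim 1). No SD is given, so effects are in SD units of the change. Equal allocation is assumed. With n per arm, two arms: d = (1.960 + 0.842) × √(2/n). Single arm: d = (1.960 + 0.842)/√n.

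| Design | Detectable d, normal | Detectable d, t-based |
|---|---|---|
| 40 in two arms of 20 | 0.886 | 0.909 |
| 20 in two arms of 10 | 1.253 | 1.325 |
| 20 in a single arm | 0.626 | 0.660 |
| 40 in a single arm | 0.443 | 0.454 |

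The plan says only large effects are detectable. Taking large as about 0.8 or more (an assumption, since the plan gives no number), this matches 40 men in two arms. It does not match the single-arm trial of 20, and it understates the limitation of a randomized trial of 20.

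**2. Shift from the ADT mix, single-arm reading.** Assumptions: the -3.60 points accrue evenly over T months, there is no drift off ADT, and the programme has no effect. The documents give neither T nor the share s on ADT. Three-month change on ADT: D = -3.60 × 3/T, which is -1.80, -0.90 and -0.45 for T = 6, 12 and 24. Shift in the pooled mean = s × D.

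| Share on ADT | T = 6 | T = 12 | T = 24 |
|---|---|---|---|
| 0.25 | -0.45 | -0.225 | -0.1125 |
| 0.50 | -0.90 | -0.45 | -0.225 |

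At the weak confidence limit the same grid runs from 0.25 × -0.47 × 3/24 = -0.015 to 0.50 × -0.47 × 3/6 = -0.118. At the strong limit it runs from 0.25 × -6.72 × 3/24 = -0.21 to 0.50 × -6.72 × 3/6 = -1.68.

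The shift can mask benefit. With half on ADT and T = 12, a true gain of 0.45 points in every man gives 0.45 - 0.45 = 0.

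**3. Whether a therapy covariate would remove it.** With two visits per man and no missing data, the time effect in a random-intercept model is the mean within-man change. A covariate that is constant within a man cancels from that difference. In a simulated set of 20 men, 10 on ADT, the time effect was -1.398 (SE 0.419) both without and with an ADT main effect. Adding ADT-by-time gave -0.677 off ADT and -2.119 on ADT, the two subgroup mean changes; their average is (-0.677 - 2.119)/2 = -1.398. Only the interaction separates the groups.

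**4. Randomized reading.** The ADT trend cancels in expectation from the between-group difference, and chance imbalance remains. With 10 of 20 men on ADT and 10 per arm, a split of 7 versus 3 or worse has hypergeometric probability 0.179. A 7 versus 3 split shifts the difference by (0.7 - 0.3) × |D| = 0.72, 0.36 or 0.18 points for T = 6, 12 or 24.

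**5. Precision of a split by ADT status.** The 95% half-width is t(0.975, n-1)/√n in SD units: 0.468 for 20 men, 0.715 for 10 and 1.242 for 5.

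**The case against.** The strongest reply is that most passages describe a randomized trial, and a comparator largely removes the ADT problem. That is right, and it is why reconciling the design comes first. It does not dispose of the point, because the aim that defines the primary outcome is explicitly single-arm.

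A second reply is that any uncontrolled pre-post change is confounded, even if every man or no man were on ADT. This also stands. A reader might infer that the ADT mix is what blocks attribution, or that splitting by ADT status would restore it. Neither follows. The missing comparator is the main obstacle, and the ADT mix makes the estimate harder to interpret and to carry over to another population. The single-arm package includes lifestyle education, so soccer alone could not be isolated in any case.

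Third, the plan does not ignore androgen status. The testosterone value should allow the mix to be partly described after enrolment, although it is not a record of ADT dates and has no stated use. Nor does the plan commit to a main-effect-only model: how therapy type would enter is unspecified, which is the accurate criticism.

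Fourth, the size is uncertain. At an assumed SD of 2 points, the 95% half-width for 20 men is 0.468 × 2 = 0.94, wider than every shift in the table. The cited comparison also included men with other urologic conditions, so it only approximates current versus past ADT.

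Finally, this is a pilot that discloses its limited power. Low power is not the complaint.

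**Conclusion.** The documents contradict themselves on design and on N, and the power remark fits only one of the combinations described. That much needs no assumption beyond a conventional meaning of a large effect and equal allocation.

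If the trial is single-arm, the pooled BMD change cannot be read as a programme effect, and its value also depends on an ADT share that eligibility leaves open. The logic rests on the documents alone. The illustrative shift of -0.11 to -0.90 points rests on an assumed accrual period of 6 to 24 months, linear loss, no drift off ADT and a quarter to half of men on ADT. It may be close to nothing at the weak confidence limit. The documents do not show that a mix will actually be enrolled, only that one is permitted, so a claim of a known bias would go too far.

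If the trial is randomized and analysed between groups, only chance imbalance in ADT status remains.

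**What to change.** 1. Reconcile the single-arm and randomized passages and the two sample sizes, and restate the power remark for the actual design and N.
2. Record current ADT status and date of last ADT at screening, with the testosterone value as support. Say whether therapy type means this and how it enters the model.
3. Report 3-month BMD change overall and by current ADT status (an ADT-by-time term) as descriptive estimates with 95% intervals.
4. If single-arm, state that no efficacy conclusion will be drawn from the uncontrolled pre-post test, and that the ADT split does not replace a comparator.
5. If randomized, base the primary analysis on the between-group difference in BMD change and include current ADT status by time in the model.

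The cost is one screening entry, since ADT history is already needed for eligibility, plus wording. The downside is wide subgroup intervals: about 0.72 SD either side for 10 men and 1.24 SD for 5. A formal test of a 0.9-point difference between men on and off ADT, at an assumed SD of 2, would have about 16% power with 10 and 10 men and 13% with 5 and 15. The split should therefore stay descriptive.
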